**9.12.3 Primary safety endpoint**

The primary safety endpoint is the proportion of subjects with major bleeding, defined (as per ISTH guidelines), as acute clinically overt bleeding associated with one or more of the following:

- a decrease in hemoglobin of 2 g/dL or more;
- a transfusion of 2 or more units of packed red blood cells;
- bleeding that occurs in at least one of the following critical sites [intracranial, intra-spinal, intraocular (within the corpus of the eye; thus, a conjunctival bleed is not an intraocular bleed), pericardial, intra-articular, intramuscular with compartment syndrome, or retroperitoneal];
- bleeding that is fatal (defined as a bleeding event that the independent Clinical Event Adjudication Committee determined was the primary cause of death or contributed directly to death);
- bleeding that necessitates surgical intervention.

#### **9.12.4 Secondary safety endpoints**

- Proportion of subjects with a clinically relevant non-major bleeding event, defined as acute clinically overt bleeding that does not meet the criteria for major and consists of:
  - any bleeding compromising hemodynamics;
  - spontaneous hematoma larger than 25 cm^2, or 100 cm^2 if there was a traumatic cause;
  - intramuscular hematoma documented by ultrasonography;
  - epistaxis or gingival bleeding requiring tamponade or other medical intervention or bleeding from venipuncture for >5 minutes;
  - hematuria that was macroscopic and was spontaneous or lasted for more than 24 hours after invasive procedures;
  - hemoptysis, hematemesis or spontaneous rectal bleeding requiring endoscopy or other medical intervention;
  - or any other bleeding considered to have clinical consequences for a patient such as medical intervention, the need for unscheduled contact (visit or telephone call) with a physician, or temporary cessation of a study drug, or associated with pain or impairment of activities of daily life.
- Proportion of subjects with clinically relevant bleeding defined as the composite of major and clinically relevant non-major bleeding.
- Proportion of subjects who permanently and prematurely discontinued study drug due to safety reasons.

#### **9.13 Replacement policy**

No patient prematurely discontinued from the study for any reason will be replaced.

## **10 Statistical Analysis**

### **10.1 Disposition of patients**

Tables and data listings will be presented for ENR population.

The number of subjects enrolled into the study, and the number of subjects enrolled but not randomized together with the reasons for not being randomized will be summarized.

An individual data listing of the patients who did not satisfy the eligibility criteria will be presented (screening log).

The frequency of patients enrolled in each site will be tabulated by randomized treatment group and for all randomized patients combined.

A summary of analysis populations and an individual data listing of the reasons for patients' exclusion from each population will be presented.

The summaries of disposition described below will also be presented by randomization stratification factor - index event.

The number of treated patients, the number of patients who completed 6 months of study treatment, and the number of subjects discontinuing study therapy together with the reasons for discontinuation will be summarized by treatment group.

The reasons for discontinuation will be taken from the End-of-Treatment Status page of the CRF.

Discontinuations from study drug due to AEs will further be summarized by the AE type: ipsilateral proximal DVT lower limbs, contralateral proximal DVT lower limbs, DVT upper limbs, PE, bleeding, acute myocardial infarction (MI), ischemic stroke, other venous thromboembolic events, other arterial thromboembolic events, and other adverse events.

### **10.2 Demographic and other baseline characteristics**

Demographic and baseline patient characteristics will be summarized by treatment group all patients in the ITT set.

The baseline values are those measured at the Screening Visit and are the following:

- Age (years) – calculated as the difference between the year of informed consent and the year of birth.
- Gender
- Ethnicity (Hispanic or Latino / Not Hispanic or Latino)
- Race (White / Black or African American / Asian / American Indian or Alaska native / Native Hawaiian or other pacific islander / Other / Not applicable (because forbidden by the national law))
- Height (cm)
- Weight (kg)
- BMI (kg/m^2)
- Systolic Blood Pressure and Diastolic Blood Pressure (mmHg)
- Heart Rate (bpm)
- ECOG Performance Status (1 / 2 / 3 / 4 / 5)
- Pregnancy test (for females with childbearing potential):

- Done / Not done
    - Result (Negative / Positive)
- Physical examination:
  - Done / Not done
    - Result (Normal / Abnormal Clinically Significant / Abnormal Not Clinically Significant)

### **10.3 Cancer diagnosis and history**

The following variables on tumor diagnosis and history will be summarized by treatment group with default statistics for all patients in the ITT set:

- Diagnosis of cancer other than basal-cell or squamous-cell carcinoma of the skin or primary tumor or acute leukemia? (Yes / No);
- Intracerebral metastasis? (Yes / No);
- Time of diagnosis (within 6 months before the study inclusion / between 6 months and 2 years before the study inclusion);
- Treatment for cancer (None in the 6 months prior to study inclusion / at study inclusion / during 6 months prior to randomization);
- Recurrent or locally advanced metastatic cancer (Yes / No);
- Time from diagnosis (months), calculated as:  
(Date of screening visit – date of diagnosis + 1) / 30.4.
- Primary Tumor site (Biliary tract / Bladder / Bone-soft tissue / Brain / Breast / Colorectal / Esophagus / Head and neck / Hematological malignancy / Hepatocellular carcinoma / Kidney / Lung / Ovary / Pancreas / Prostate Gland / Skin – Melanoma / Skin – Basal Cell Carcinoma / Skin – Squamous Cell Carcinoma / Stomach / Testicular cancer / Thyroid / Uterus / Other)
- If hematological malignancy:
  - Type of malignancy (Acute lymphocytic leukemia / Chronic lymphocytic leukemia / Acute myeloid leukemia / Chronic myeloid leukemia / Leukemia – other / Non-Hodgkins lymphoma / Hodgkins lymphoma / Multiple myeloma / Other);
    - Complete remission (Yes / No);
- If lung, type of tumor (SCLC / NSCLC / Other)
- Histological type (Adenocarcinoma / Squamous cell carcinoma / Sarcoma / Neuroendocrine / Unknown / Not applicable / Other)
- Staging at study entry (Localized / Regional / Distant / Unknown / Not applicable)

### **10.4 Venous thromboembolism**

The following variables on venous thromboembolism characteristics will be summarized by treatment group with default statistics for all patients in the ITT set:

- Type of VTE (DVT = Deep Vein Thrombosis / PE = Pulmonary Embolism)
- Time from confirmed diagnosis (months), calculated as: (date of screening visit – date of confirmed diagnosis +1)/30.4.

- Symptomatic (Yes / No)
- If type of VTE is DVT:
  - Specific type of DVT (Symptomatic DVT proximal lower limb / Unsuspected DVT proximal lower limb)
  - Location of DVT (Vena Cava, Vena iliaca right / Vena iliaca left / Vena iliaca bilateral, Right femoral vein / Left femoral vein / Bilateral femoral vein, Right popliteal vein / Left Popliteal vein, / Bilateral Popliteal vein, Right Distal vein / Left Distal vein / Bilateral Distal vein, Other)
  - If symptomatic, type of symptoms (Pain, Redness, Calf pain of tenderness, Swelling of extremities, Tenderness along deep vein, Additional relevant DVT findings)
  - Confirmatory tests (Compression ultrasonography, Venography, CT Venography, MR Venography, Other)
- If type of VTE is PE:
  - Specific type of PE (Symptomatic PE / Unsuspected PE in a segmental or more proximal pulmonary artery)
  - Location of PE (Right Pulmonary Artery / Left Pulmonary Artery, Bilateral Pulmonary Artery, Trunk, Right lobar branch / Left Lobar Branch / Bilateral Lobar Branches, Segmentary-Subsegmentary artery, Other)
  - If symptomatic, type of symptoms (Breathing difficulties including dyspnea or tachypnea, Chest Pain, Cough, Hemoptysis, Tachycardia, Fever, Cyanosis, Additional relevant PE findings)
  - Confirmatory tests (CT pulmonary angiography, Pulmonary angiogram, VQ scan, Perfusion scan, Echocardiogram, Other).

## 10.5 Medical history and comorbidities

Data will be summarized for ITT analysis set by treatment group with descriptive statistics.

Previous diseases are those reported as “*Not ongoing*” whereas the Concomitant Diseases are those reported as “*ongoing*” in eCRF.

All verbatim terms will be assigned to a Preferred Term (PT) and will be classified by primary System Organ Class (SOC) according to the MedDRA thesaurus version 20.1.

The following data will be presented:

1. a default frequency tabulation of patients who exhibited at least one previous disease by treatment group;
2. a frequency table showing the previous diseases by primary System Organ Class and Preferred Term by treatment group;
3. a default frequency tabulation of patients who exhibited at least one concomitant disease by treatment group;
4. a frequency table showing the concomitant diseases by primary System Organ Class and Preferred Term by treatment group.

## 10.6 Previous and concomitant medications

All medications will be coded using the WHO-DRL Dictionary (DD) B2-format version 2017 and

classified according to 3rd level ATC subgroup (Primary therapeutic subgroup) and generic name. Concomitant medications are those reported in the eCRF “Concomitant Treatments” form and include all medications with start date on or after the study medication start date and all medications taken prior to the study entry and still taken after the study medication start date.

Previous medications are those reported in the eCRF “Concomitant Treatments” form with end date before the date of first study drug administration.

Previous and concomitant medications will be summarized by treatment group for the ITT set.

Medications started after the date of end of study treatment will be considered as post-study treatments and they will be only listed.

## **10.7 Study drug**

Data will be summarized by treatment group for mITT set with descriptive statistics.

Descriptive analyses will be presented by treatment group for:

- The study drug amount administered (amount dispensed – amount returned);
- The duration of treatment administration (calculated, in weeks, as (date of last dose – date of first dose +1) / 7);
- Compliance (calculated by the system outside the eCRF).

## **10.8 Analysis of efficacy**

### **10.8.1 Analysis of primary endpoint**

Analyses of the primary efficacy endpoint will be performed using the modified intent-to-treat (mITT) analysis set, the intent-to treat (ITT) analysis set and the per protocol (PP) analysis set.

The mITT and the ITT analyses of the primary endpoint will include endpoints that occur at any time from randomization until the end of the originally intended treatment period regardless of whether subjects were receiving study medication.

The analysis performed on the mITT population will be considered as the primary whereas the analyses performed in the ITT and PP population will be seen as supportive (sensitivity analysis).

The primary efficacy variable, i.e. the time from randomization to the first recurrent thromboembolic event (days), will be analyzed after adjusting estimates for the competing risk of death unrelated to VTE. The competing risk analysis will be performed using the SAS procedure PHREG while the probabilities of failure for the event of interest (first recurrent thromboembolic event) are displayed using cumulative incidence plots which do account for the competing risk (death unrelated to VTE). Patients without recurrent thromboembolic event will be censored at 6- month (i.e. Day 180).

The null hypothesis to be tested will be that apixaban is inferior to dalteparin in the prevention of recurrent thromboembolic events during 6-month follow-up; i.e.  $H_0 \rightarrow E[HR] \geq 2.00$ .

The alternative hypothesis will be that apixaban is non-inferior to dalteparin in the prevention of recurrent thromboembolic events during 6-month follow-up; i.e.  $H_a \rightarrow E[HR] < 2.00$ .

Where:  $E[HR]$  is the Expected (E) apixaban-to-comparator Hazard Ratio (HR), while 2.00 is the prefixed non-inferiority threshold.

The evaluation of the primary objective will be done by considering the time from randomization to the first recurrent thromboembolic event (event of interest) or to the occurrence of death unrelated

to VTE (nuisance/competing event) or to the last follow-up if neither a recurrent thromboembolic event nor a competing event occurred within the 6-month follow-up (censored time). The apixaban-to-comparator Hazard Ratio adjusted for the competing risk of death unrelated to VTE will be computed with associated two-sided 95% confidence interval by resorting to the Fine & Gray regression model using treatment group, center, symptomatic vs unsuspected VTE and active cancer vs history of cancer as dummy covariates. Apixaban will be considered non-inferior to the comparator dalteparin if the upper two-sided 95% confidence limit of Hazard ratio is < 2.00.

Number and percentage of events of interest, competing events and censored patients will be presented as summary of failure outcome. Degrees of freedom (DF), Wald Chi-square and the associated p-value derived from the PHREG model will be also presented.

Superiority of apixaban vs. dalteparin will be tested as a secondary analysis of the primary endpoint, only after non-inferiority has been demonstrated for the experimental treatment group (apixaban) relative to the conventional treatment group (dalteparin). According to CPMP/EWP/482/99 document entitled: "*Points to consider on switching between superiority and non-inferiority*", switching the apixaban vs. dalteparin contrast from the non-inferiority objective to the superiority objective is feasible because the trial is properly designed in accordance to the strict requirements of a non-inferiority trial.

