With the use of an estimated incidence of the primary efficacy outcome of 7% at 6 months with dalteparin and an upper non-inferiority margin of 2.00 for the hazard ratio, we calculated that we would need to enroll 934 completer patients for the study to have 80% power to show the non-inferiority of apixaban, at a one-sided alpha level of 0.025. This sample will be increased to 1168 patients to account for up to 20% lost in total patient-years. This estimate is consistent with a drop-out rate of 40% assuming patients discontinued uniformly during the follow-up (mean discontinuation time equal to 3 months)

Statistical Analysis:

Analysis of the Primary Study Outcome

The primary efficacy data set will consist of all randomized subjects who received at least one dose of the study drugs (modified intent-to treat population) with a non-missing primary outcome. Subjects will be categorized to the group to which they were assigned at randomization, regardless of the treatment actually received.

Caravaggio Study Protocol FINAL Version 3.0, May 22nd 2018

The secondary efficacy data sets will consist of a) all randomized subjects (intent-to treat population) and b) the per-protocol population (defined in the SAP).

The safety data set will consist of all treated subjects (randomized subjects who received at least one dose of study drug).

The primary efficacy variable, i.e. the time from randomization to the first recurrent thromboembolic event, will be analyzed after adjusting estimates for the competing risk of death unrelated to VTE.

The evaluation of the primary objective will be done by considering the time from randomization to the first recurrent thromboembolic event (event of interest) or to the occurrence of death unrelated to VTE (nuisance/competing event) or to the last follow-up if neither a recurrent thromboembolic event nor a competing event occurred within the intended 6-month study treatment period (censored time).

Analyses of the primary efficacy endpoint will be performed using the modified intent-to-treat principle, the intent-to treat principle and the per protocol principle. The modified intent-to-treat and the intent-to-treat analyses of the primary endpoint will include endpoints that occur at any time from randomization until the end of their originally intended treatment period regardless of whether subjects were receiving study medication.

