- assess study medication use;
- measure the body weight;
- dispense study medication assigned for the current visit;
- assess concomitant medication use;
- for patients with study outcomes investigators should provide documentation for the recurrent VTE event (qualifying imaging) within four weeks.

At 6-month follow-up visit or end of study treatment:

The investigator or delegate will:

• assess study outcomes (i.e. suspected recurrent VTE, bleeding), including subjects who have discontinued study treatment. For subjects who have discontinued study

treatment, telephone query of health status (alive, occurrence of efficacy and safety endpoints and AEs/SAEs) is allowed. Subjects who have new symptoms should undergo further assessment as clinically appropriate, preferably at the study site whenever feasible.

• check the following local laboratory results:

Serum chemistry

- Total bilirubin (direct and indirect)
- Alanine transaminase (ALT)
- Aspartate transaminase (AST)
- Alkaline phosphatase (ALP)
- Serum creatinine
- CrCL

Hematology and platelet count

- Hematocrit
- White blood cell (WBC) count
- Hemoglobin
- Platelet count;
- collect study medication dispensed at previous visit;
- assess study medication use;
- assess concomitant medication use:
- for patients with study outcomes investigators should provide documentation for the recurrent VTE event (qualifying imaging) within four weeks.
- assess Quality of Life (QoL) by means of the Anti-Clot Treatment Scale (ACTS) at the end of the study treatment.

At 7-month after randomization:

The investigator or delegate will:

- assess for AE/SAE(s)
- for patients with study outcomes investigators should provide documentation for the recurrent VTE event (qualifying imaging) within four weeks.
- assess efficacy and safety (i.e. recurrent VTE, major bleeding), including subjects who have discontinued study treatment. Query of health status (alive, occurrence of efficacy endpoints and SAEs) and current anticoagulant treatment by telephone is allowed.

Unscheduled Visit:

An unscheduled visit may occur during the study treatment period, at any time the Investigator considers it might be necessary.

The procedures and assessments performed during an unscheduled visit strictly depends by the reason why such visit occurs.

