6.5.2 Withdrawal of Consent from Study Participation

In accordance with the Declaration of Helsinki and other applicable regulations, a subject has the right to withdraw consent from study participation at any time and for any reason without prejudice to his or her future medical care by the physician or at the institution. However, it is important to distinguish between withdrawal of consent with regards to continuing on study medication (but continuing to be followed on study) versus withdrawal of consent with regards to discontinuing the study all together (i.e., withdrawal of consent with regards to continuing on study medication and any further study follow-up).

Only subjects who refuse all 4 of the following methods of follow-up will be considered to have withdrawn consent from study participation:

- Participation in the trial follow-up visits per protocol, either in clinic or by telephone;

- Contact by trial personnel even if only by telephone;
- Permission for trial personnel to contact an alternative person (e.g., family member, spouse, partner, legal representative, physician, the anticoagulation clinic, or another healthcare provider) even if only by telephone;
- Permission for trial personnel to access and review their medical information from alternative sources (e.g., doctor's notes, hospital records).

If the subject refuses all 4 of the above methods of follow-up, the investigator should personally speak to the subject to ensure the subject understands all the potential methods of follow-up. If the subject continues to refuse all potential methods of follow-up, the Investigator will document this as a withdrawal of consent in the medical record.

All subjects should be followed for the full duration of the trial using any or all of the above methods, unless there is written documentation by the investigator of the subject's withdrawal of consent to ALL of the above methods of follow-up.

The site will complete and report the observations as thoroughly as possible up to the date of consent withdrawal and including the date of the final dose of study drug. The reason(s) for limited follow-up/data collection will be clearly documented in the medical record and eCRF.

Public databases and subject finder services may be used to determine subject status and to locate potential lost to follow-up patients.

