#### 10.8.2 Analysis of secondary endpoints

For the secondary efficacy endpoints, analyses will be performed using the mITT analysis set.

- The individual components of the primary efficacy outcome (Proximal DVT of the lower limbs (symptomatic or unsuspected), DVT of the upper limb (symptomatic), and PE (symptomatic or unsuspected)): The same competing risk model defined in paragraph 10.8.1 for the analysis of primary efficacy variable will be employed for the analysis of the time (in days) from randomization to the first recurrent event among those included in the primary efficacy outcome recurrent (see Paragraph 9.12.1). The apixaban-to-comparator Hazard Ratio adjusted for the competing risk of death unrelated to VTE will be computed with associated two-sided 95% confidence interval. If neither the event of interest nor a competing event occurred within the 6-month follow-up, the patient will be censored at 6-month follow-up.
- Symptomatic recurrence of VTE: The same competing risk model defined in paragraph 10.8.1 for the analysis of primary efficacy variable will be employed for the analysis of the time (in days) from randomization to the first symptomatic recurrent thromboembolic event. The apixaban-to-comparator Hazard Ratio adjusted for the competing risk of death unrelated to VTE will be computed with associated two-sided 95% confidence interval. If neither the event of interest nor a competing event occurred within the 6-month follow-up, the patient will be censored at 6-month follow-up.
- Composite of primary efficacy outcome plus major bleeding: The competing risk model defined in paragraph 10.8.1 for the analysis of primary efficacy variable will be employed for the analysis of the time (in days) from randomization to the composite of primary efficacy outcome (see Paragraph 9.12.1) plus major bleeding. The apixaban-to-comparator Hazard Ratio adjusted for the competing risk of death unrelated to VTE or major bleeding will be computed with associated two-sided 95% confidence interval. If neither the event of interest nor a competing event occurred within the 6-month follow-up, the patient will be

censored at 6-month follow-up.

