- Any fatal or not fatal cardiovascular event: The competing risk model defined in paragraph 10.8.1 for the analysis of primary efficacy variable will be employed for the analysis of the time (in days) from randomization to the occurrence of any fatal or not fatal cardiovascular event. The apixaban-to-comparator Hazard Ratio adjusted for the competing risk of death unrelated to cardiovascular event will be computed with associated two-sided 95% confidence interval. Number and percentage of events of interest, competing events and censored patients will be presented as summary of failure outcome. Degrees of freedom (DF), Wald Chi-square and the associated p-value derived from the PHREG model will be also presented. Subjects with no events at the end of the study will be censored at the date of the last contact.
- All venous thromboembolic events (including splanchnic vein thrombosis and cerebral vein thrombosis): The same competing risk model defined in paragraph 10.8.1 for the analysis of primary efficacy variable will be employed for the analysis of the time (in days) from

randomization to thromboembolic events at sites other than DVT and PE. The apixaban-to-comparator Hazard Ratio adjusted for the competing risk of death unrelated to venous thromboembolic events will be computed with associated two-sided 95% confidence interval. Number and percentage of events of interest, competing events and censored patients will be presented as summary of failure outcome. Degrees of freedom (DF), Wald Chi-square and the associated p-value derived from the PHREG model will be also presented. Subjects with no events at the end of the study will be censored at the date of the last contact.

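### SAP 10.8.1 sets two different censoring times for event-free patients lost before Day 180, and one of them counts unobserved time as event-free

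*SAP*

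**What the plan says.** SAP 10.8.1 defines the primary variable as time from randomization to first recurrent VTE, with death unrelated to VTE as the competing event. It gives the censoring time twice.

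- First: "Patients without recurrent thromboembolic event will be censored at 6- month (i.e. Day 180").
- Later in the same section, time runs to recurrence, to death unrelated to VTE, "or to the last follow-up if neither a recurrent thromboembolic event nor a competing event occurred within the 6-month follow-up (censored time").

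Protocol section 10.6 carries only the last-follow-up rule. So does the protocol synopsis, which censors at last follow-up "if neither a recurrent thromboembolic event nor a competing event occurred within the intended 6-month study treatment period (censored time"). The Day-180 sentence appears only in the SAP.

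SAP 10.8.2 repeats the six-month wording in three bullets (individual components, symptomatic VTE, and VTE plus major bleeding): "If neither the event of interest nor a competing event occurred within the 6-month follow-up, the patient will be censored at 6-month follow-up".

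SAP 10.8.1 also restricts mITT and ITT endpoints to the originally intended treatment period, whether or not the patient is still on study drug.

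**The concern.** Take a patient with no recurrence who is last heard from on Day 60. The first rule censors at Day 180 and the second at Day 60. No sentence says which one governs or that the earlier date applies. Under the first rule the patient stays in the risk set for 120 days in which a recurrence could not have been recorded.

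Neither rule adds or removes an observed recurrence; only the time at risk changes. The stake is therefore limited to two things: the cumulative incidence curves, and the hazard ratio that is compared with the margin of 2.00. The hazard ratio is affected only when loss of outcome follow-up is unequal between arms. In an open-label trial, the rule should still have a single meaning before the analysis is programmed.

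**Working it through.** **Inputs from the documents.** Dalteparin incidence 7% at 6 months, margin 2.00, one-sided alpha 0.025, power 80%, 934 completers inflated to 1,168 (protocol 10.1, SAP 9.3), 1:1 allocation, so 584 per arm.

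**The plan's own figure.** Events = 4 × (1.960 + 0.842)² / (ln 2)² = 65.35. Then 65.35 / 0.07 = 933.5, or 934; and 934 / 0.80 = 1,167.5, or 1,168. The 20% is 40% × 3/6. These figures reproduce and do not depend on the censoring rule.

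**Assumptions.** The documents give no expected loss of outcome follow-up, so each loss rate L below is an assumption, taken over 2% to 5%. Time to recurrence is exponential, loss is uniform over 180 days, and competing deaths, center and strata are ignored.

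**Step 1: risk observed under the literal Day-180 rule.** Let p be the true 180-day risk and h = −ln(1 − p). The average risk observed in a patient lost at a uniform time is 1 − p/h. The crude risk is

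(1 − L) × p + L × (1 − p/h).

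- Dalteparin: p = 0.0700, h = 0.07257, 1 − p/h = 0.03542.
- Apixaban at a true hazard ratio of 2.00: p = 1 − 0.93² = 0.1351, h = 0.14514, 1 − p/h = 0.06918.

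Dalteparin with 5% loss: 0.95 × 0.0700 + 0.05 × 0.03542 = 0.0683. A true 7.0% reads 6.8%.

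**Step 2: hazard ratio as read.** With every non-event carried to Day 180, HR ≈ ln(1 − crude risk, apixaban) / ln(1 − crude risk, dalteparin).

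**Step 3: chance of declaring non-inferiority.** SE = √(1/e_A + 1/e_D), with e = 584 × crude risk; P = Φ((ln 2 − ln HR)/SE − 1.96).

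Worked case, 3% loss on apixaban and 5% on dalteparin, true hazard ratio 2.00:

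- Crude risks: 0.97 × 0.1351 + 0.03 × 0.06918 = 0.1331, and 0.0683.
- HR = 2.020; events 77.7 and 39.9; SE = 0.195.
- P = Φ(−0.052 − 1.960) = 2.2%.

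| Assumed loss, apixaban / dalteparin | HR read (true 2.00) | False non-inferiority (correct 2.5%) |
|---|---|---|
| 3% / 2% | 1.99 | 2.7% |
| 2% / 3% | 2.01 | 2.4% |
| 5% / 3% | 1.98 | 2.9% |
| 3% / 5% | 2.02 | 2.2% |
| 5% / 5% | 2.00 | 2.5% |

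At a true hazard ratio of 1.00 with 3% / 5% loss, the crude risks are 6.90% and 6.83%, the hazard ratio reads 1.01, and power is 86% against 87% with correct censoring.

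**The case against.** The best defense is that the intent is easy to guess. The last-follow-up clause comes from the protocol, the endpoint window is six months, and a sensible programmer would take the earlier of the two dates. That is probably right, and it keeps the point minor. But it is not written, and the repetition of the six-month wording in three bullets of SAP 10.8.2 makes the literal Day-180 coding a plausible outcome.

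It is also fair to say that early loss should be rare. Protocol 6.5.2 states "Only subjects who refuse all 4 of the following methods of follow-up will be considered to have withdrawn consent from study participation", and protocol 6.6 keeps patients who stop study drug in follow-up for seven months. This stands.

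A reader might infer more than the documents support, in four ways:

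- **That last follow-up is open-ended.** The seven-month visit does collect outcomes ("assess efficacy and safety (i.e. recurrent VTE, major bleeding), including subjects who have discontinued study treatment"), and no sentence caps the censoring date itself. But endpoints count only within the intended six-month period, and a censoring date after Day 180 changes no risk set up to Day 180. The hazard ratio is unaffected.
- **That deaths would be censored at Day 180.** The Day-180 sentence does not exempt them. But the same section times these deaths as competing events and requires that "Number and percentage of events of interest, competing events and censored patients will be presented as summary of failure outcome". The parallel bullets in 10.8.2 exempt competing events explicitly.
- **That the 40% drop-out in the sample-size section is the loss rate.** That figure describes patients who discontinue, and discontinued patients are still followed. No large loss of outcome follow-up can be derived from it.
- **That last-contact censoring elsewhere in 10.8.2 is a further conflict.** Where it appears ("Subjects with no events at the end of the study will be censored at the date of the last contact"), it governs other endpoints and does not contradict the primary rule.

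**Conclusion.** The conflict is real: one section gives two censoring times for the primary variable, and they diverge for event-free patients lost before Day 180. The Day-180 rule is wrong as written for those patients.

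The expected effect is small. Over the assumed 2% to 5% loss, cumulative incidence is understated by at most about 0.2 percentage points at a true 7.0%. Equal loss leaves the hazard ratio essentially unchanged. Unequal loss moves a true 2.00 to between 1.98 and 2.02, and false non-inferiority to between 2.2% and 2.9%. The direction depends on which arm loses more patients.

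These sizes rest on assumed loss rates, an exponential hazard and uniform loss. That the two rules differ rests on the text alone. Severity: minor.

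**What to change.** In SAP 10.8.1, replace both the Day-180 sentence and the last-follow-up clause with one rule:

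> Patients with neither a recurrent VTE nor a death unrelated to VTE on or before Day 180 are censored at the earlier of the last contact at which outcome status was known and Day 180. Death unrelated to VTE is a competing event at its date.

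Make the matching edit to the three bullets in SAP 10.8.2 that now censor at six-month follow-up, each with its own event and competing death.

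The cost is one replacement rule and three short edits. No new data are needed, since SAP 10.8.2 already uses last-contact dates for other endpoints. The sample sizes of 934 and 1,168 do not change.
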